6.4.5 Adverse Events

6.4.5.1 Definitions of Adverse Events

An AE is any adverse change from the subject's baseline conditions, ie, any unfavorable and unintended sign, including an abnormal laboratory findings, symptoms or disease, that occurs during the course of the study, whether or not considered related to the study drug.

A TEAE is defined as any event not present before exposure to study drug or any event already present that worsens in either intensity or frequency from study drug initiation until after the last dose of study drug whether or not considered related to the study drug. The

Investigator is responsible for reporting all TEAEs that are observed or reported during the study, regardless of their relationship to study drug or their clinical significance.

An elective surgery/procedure scheduled to occur during the study will not be considered an AE if the surgery/procedure is being performed for a pre-existing condition and the surgery/procedure has been pre-planned prior to study entry.

6.4.5.2 Serious Adverse Events

An SAE is defined as any event that results in death, is immediately life-threatening, requires inpatient hospitalization or prolongation of existing hospitalization, results in persistent or significant disability/incapacity, or is a congenital anomaly/birth defect.

Important medical events that may not result in death, be life-threatening, or require hospitalization may be considered SAEs when, based upon appropriate medical judgment, they may jeopardize the subject or require medical or surgical intervention to prevent one of the outcomes listed in this definition. Examples of such medical events include an allergic bronchospasm requiring intensive treatment in an emergency room or at home, blood dyscrasias, convulsions that do not result in inpatient hospitalization, or the development of drug dependency or drug abuse.

Note: The AE terms neutropenia and hypertension should be used only when reporting events that meet the following criteria:

- The term neutropenia is reserved for reporting an absolute neutrophil count (ANC) $<1500/\text{mm}^3$ or $<1.5 \times 10^9/\text{L}$ and may or may not be associated with fever or concurrent infection.
- The term hypertension is reserved for reporting an increase in systolic blood pressure $>160 \text{ mm Hg}$, or diastolic blood pressure $>100 \text{ mm Hg}$, or any clinically significant increase in blood pressure that requires modification of the subject's antihypertensive regimen.

6.4.5.3 Eliciting and Documenting Adverse Events

Adverse events will be assessed and reported from the time the subject takes the first dose of IMP until and including the EOS visit (Visit 7).

All SAEs occurring after signing the ICF must be reported (whether considered associated or not associated to study design or study-mandated procedures).

If the Investigator becomes aware of an SAE that occurs after the EOS visit and is assessed by the Investigator as at least possibly related to the study drug, they need to report the SAE.

At every study visit, subjects will be asked a standard nonleading question to explore a response regarding any medically related changes in their well-being. They will also be asked if they have been hospitalized, had any accidents, used any new medications, or changed concomitant medication regimens (both prescription and over-the-counter medications).

In addition to subject observations, AEs identified from any study data (eg, laboratory values, physical examination findings, ECG changes) or identified from review of other documents that are relevant to subject safety will be documented on the AE page in the eCRF.

6.4.5.4 Reporting Adverse Events

All AEs reported or observed during the study will be recorded on the AE page in the eCRF. Information to be collected includes drug treatment, dose, event term, time of onset, Investigator-specified assessment of severity and relationship to study drug, time of resolution of the event, seriousness, any required treatment or evaluations, and outcome.

Adverse events resulting from concurrent illnesses, reactions to concurrent illnesses, reactions to concurrent medications, or progression of disease states must also be reported. Any medical condition that is present at the time that the subject is screened but does not deteriorate should not be reported as an AE. However, if it deteriorates at any time during the study, it should be recorded as an AE.

All AEs will be followed to adequate resolution. The Medical Dictionary for Regulatory Activities (MedDRA) will be used to code all AEs.

6.4.5.5 Reporting Serious Adverse Events

Any AE that meets SAE criteria (Section 6.4.5.2) must be reported to PPD Pharmacovigilance (PVG) immediately (ie, within 24 hours) after site personnel are aware of the event. This must be done via the eCRFs on the AE page. The entry will automatically be

sent to the PPD PVG team for review. If the eCRF system is unavailable, a manual SAE form may be used and faxed to the numbers outlined below.

The nonserious adverse event of special interest (AESI) defined in Section 6.4.5.6 should be recorded in the eCRF using the same process as for reporting SAEs.

The following contact information is to be used for PPD PVG:

PVG [contact]/[contact]

PVG Fax line: [contact]/[contact] or [contact]

6.4.5.6 Suspected Unexpected Serious Adverse Reactions and Nonserious Adverse Events of Special Interest

The following nonserious AESI should be recorded on the eCRF using the same process as for reporting SAEs.

- **Neutropenia** with fever defined as ANC <1500/mm³ or <1.5 × 10⁹/L on the most recent complete blood count with fever equal to or greater than 38°C that does not fulfill any of the serious criteria, ie, hospitalization.
- **Hepatotoxicity** defined as ALT >3 × ULN plus total bilirubin >2 × ULN that does not fulfill any of the serious criteria, ie, hospitalization. This information should be recorded on the drug induced liver injury eCRF each time the elevated laboratory parameters are met during the study.

Oscotec Inc. will promptly evaluate all suspected unexpected serious adverse reactions (SUSARs) and nonserious AEs of special interest against cumulative product experience to identify and expeditiously communicate possible new safety findings to Investigators, institutional review board (IRBs)/independent ethics committee (IECs), and applicable health authorities based on applicable legislation.

To determine reporting requirements for single AE cases, Oscotec Inc. will assess the expectedness of these events using the study drug Investigator's brochure. Reporting requirements will also be based on the Investigator's assessment of causality and seriousness, with allowance for upgrading by Oscotec Inc. as needed.

Osco Inc. will compare the severity of each SUSAR and the cumulative event frequency reported for the study with the severity and frequency reported in the applicable reference document.

6.4.5.7 Assessment of Severity

The severity, or intensity, of an AE refers to the extent to which an AE affects the subject's daily activities. The intensity of the AE will be rated using the following criteria:

- Grade 1 No interference with activity
- Grade 2 Some interference with activity not requiring medical intervention
- Grade 3 Prevents daily activity and requires medical intervention
- Grade 4 Emergency room visit or hospitalization
- Grade 5 Fatal

Changes in the severity of an AE should be documented to allow an assessment of the duration of the event at each level of intensity to be performed. Adverse events characterized as intermittent do not require documentation of the onset and duration of each episode.

6.4.5.8 Assessment of Causality

The Investigator's assessment of an AE's relationship to study drug is part of the documentation process, but it is not a factor in determining what is or is not reported in the study. If there is any doubt as to whether a clinical observation is an AE, the event should be reported.

The relationship or association of the study drug in causing or contributing to the AE will be characterized using the following classification and criteria:

- Unrelated: This relationship suggests that there is no association between the study drug and the reported event.
- Possible: This relationship suggests that treatment with the study drug caused or contributed to the AE, ie, the event follows a reasonable temporal sequence from the time of drug administration or follows a known response pattern to the study drug but could also have been produced by other factors.

Probable: This relationship suggests that a reasonable temporal sequence of the event with drug administration exists and, based upon the known pharmacological action of the drug, known or previously reported adverse reactions to the drug or class of drugs, or judgment based on the Investigator's clinical experience, the association of the event with the study drug seems likely. The event disappears or decreases on cessation or reduction of the dose of study drug.

Definite: This relationship suggests that a definite causal relationship exists between drug administration and the AE, and other conditions (concurrent illness, progression/expression of disease state, or reaction to concurrent medication) do not appear to explain the event. The event reappears or worsens if the study drug is re-administered.

6.4.5.9 Follow-Up of Subjects Reporting Adverse Events

All AEs must be reported in detail on the appropriate page in the eCRF and followed until a satisfactory resolution, until the Investigator deems the event to be chronic or not clinically significant, or until the subject's condition is considered to be stable.

6.5 Pharmacokinetic Assessments

6.5.1 Pharmacokinetic Blood Samples

Timepoints for Sample Collection

Serial blood samples for PK assessment of SKI-O592 and its metabolites (M2 and M4) will be collected in a subset of subjects at the following time points (Table 6-2):

- Day 1: 0 hour (predose), at 15 (+5 minutes) and 30 minutes (± 5 minutes), 1 hour, 2, 4, 8, and 12 hours (± 10 minutes) postdose (12 hour sample should be collected prior to the evening dose).
- Trough: predose samples will be collected pre-morning on Day 14 (Weeks 2), Day 28 (Week 4), and Day 56 (Week 8).
- Day 84 (Week 12): 0 hour (predose), at 15 (+5 minutes) and 30 minutes (± 5 minutes), 1 hour, 2, 4, 8, and 12 hours (± 10 minutes) after administration of the morning dose.

Clinical staff is encouraged to take the blood samples for PK analysis at the scheduled time points listed above. The exact time and date of the blood draw must be recorded using an unambiguous format such as DD MON YYYY and HH:MM using a 24-hour clock.

When the PK blood sample collection coincides with safety assessments, PK blood samples should be collected as close to the scheduled time point as possible and safety assessments should be performed before PK blood samples are taken.

Processing of Blood Samples

For each sample collected, separated plasma will be transferred in approximately equal portions into 2 tubes that are labeled for sets A and B for SKI-O-592 and metabolites.

Set A samples will be transported, frozen with sufficient dry ice for several days, to the bioanalytical facility.

Set B samples will be retained at the study site until the study is completed, unless shipment to another facility is requested by Oscotec Inc. Instructions regarding the disposition of the B samples will be provided by Oscotec Inc. Plasma samples will be stored at approximately –70°C in an upright position.

Specific details and the full protocol for analysis of PK samples can be found in the study laboratory manual.

6.5.2 Pharmacokinetic Variables

Plasma PK parameters will be calculated for SKI-O-592 and metabolites M2 and M4 using a noncompartmental approach and will include the following, where applicable:

C_{max}	maximum observed concentration
T_{max}	time to reach the maximum observed concentration
$AUC_{0-\tau}$	area under the concentration versus time curve within a dosing interval
$t_{1/2}$	apparent terminal elimination half-life
K_{el}	terminal elimination rate constant
CL/F	apparent oral clearance (SKI-O-592 only)

V_z/F apparent oral volume of distribution (SKI-O-592 only)

R_{met} metabolite ratio

R_{AUC} accumulation ratio based on $AUC_{0-\tau}$

Additional PK parameters may be estimated, as deemed appropriate.

6.6 Pharmacodynamic Assessments

6.6.1 Pharmacodynamic Blood Samples

Timepoints for Sample Collection

Serial blood samples for assessment of the percentage of activated gp53/CD63+ basophils in peripheral blood will be collected in the same subset of subjects for whom PK sample will be collected (Table 6-2):

- Day 1: 0 hour (predose), at 30 minutes (± 5 minutes), 1 hour, 2, 4, 8 and 12 hours (± 10 minutes) postdose (12 hour sample should be collected prior to the evening dose)
- Trough: predose samples will be collected pre-morning on Day 14 (Week 2), Day 28 (Week 4), and Day 56 (Week 8)
- Day 84 (Week 12): 0 hour (predose), at 30 minutes, 1 hour, 2, 4, 8, and 12 hours (± 10 minutes) after administration of the morning dose

Clinical staff is encouraged to take the blood samples for PD analysis at the scheduled time points listed above. The exact time and date of the blood draw must be recorded using an unambiguous format such as DD MON YYYY and HH:MM using a 24-hour clock.

Processing of Samples

The samples must be dispatched to the processing laboratory as quickly as possible to ensure transport, cataloging, and processing is complete within the required timeframe for the selected assay.

Specific details and the full protocol for analysis of PD samples can be found in the study laboratory manual.

6.6.2 Pharmacodynamic Variables

The primary PD endpoint will be the change in the percentage of activated gp53/CD63+ basophils in peripheral blood. PD parameters will include the following:

E_{max} maximum effect

TE_{max} time to achieve maximum effect

$AUEC_{0-\tau}$ area under the effect versus time curve within a dosing interval

Additional PD endpoints/parameters may be evaluated, as deemed appropriate.

Table 6-2
Pharmacokinetic and Pharmacodynamic Schema

	Dose Reference Timing*	Predose (0 hour)	15 min (+5 min)**	30 min (±10 min)	1 h (±10 min)	2 h (±10 min)	4 h (±10 min)	8 h (±10 min)	12 h (±10 min)
Visit 1: Day 1									
PK Sample Volume	AM	X	X	X	X	X	X	X	X
PD Sample Volume	AM	X	X	X	X	X	X	X	X
Visit 2: Day 14									
PK Sample Volume	AM	X							
PD Sample Volume	AM	X							
Visit 3: Day 28									
PK Sample Volume	AM	X							
PD Sample Volume	AM	X							
Visit 4: Day 56									
PK Sample Volume	AM	X							
PD Sample Volume	AM	X							
Visit 5: Day 84									
PK Sample Volume	AM	X	X	X	X	X	X	X	X
PD Sample Volume	AM	X	X	X	X	X	X	X	X

Abbreviations: PD, pharmacodynamic; PK, pharmacokinetic.

* Sampling should be performed after AM (morning) dose only.

** Applicable for PK samples only.

6.7 Safety Monitoring Committee

No formal safety monitoring committee will be established for the study.

6.8 Pregnancy

Subjects must be counseled during the informed consent process to inform the investigator of any pregnancy that occurs during study participation and for 6 months after the last dose of study drug. In the event of an unexpected pregnancy during study participation or for 6 months after the last dose of study drug, it must be reported via fax or email to PPD within 24 hours of the study site knowledge of the pregnancy via manual Initial Pregnancy Report Form.

For a female subject, the study drug must be discontinued immediately and the subject should inform the Investigator as soon as possible (see Section 4.2). Although study drug will be discontinued, the subject may choose to remain in study and will continue to be monitored for safety while following their regular visit schedule. If the partner of a male subject becomes pregnant, the male subject is not required to discontinue study drug and may remain on the study. The male subject is responsible for informing his partner(s) of the risk of becoming pregnant and for reporting any pregnancy to the Investigator.

The pregnancy must be followed up to determine the outcome (including spontaneous miscarriage, elective termination, normal birth, or congenital abnormality) and the status of mother and child, even if the subject was discontinued from the study, and should be reported to PPD via fax or email on the manual follow-up pregnancy form.

Pregnancy complications and elective terminations for medical reasons must be reported as AEs or SAEs. Spontaneous miscarriages must be reported as SAEs.

Any SAE occurring in association with a pregnancy that is brought to the Investigator's attention after the subject has completed the study and that is considered by the Investigator as possibly related to the study drug must be promptly reported to the sponsor.

6.9 Laboratory Analyses

Any abnormal laboratory test results (hematology, clinical chemistry, or urinalysis) or other safety assessments (eg, ECGs, radiological scans, vital sign measurements), including those

that worsen from baseline, felt to be clinically significant in the medical and scientific judgment of the Investigator are to be recorded as AEs or SAEs.

However, any clinically significant safety assessments that are associated with the underlying disease, unless judged by the Investigator to be more severe than expected for the subject's condition, are **not** to be reported as AEs or SAEs.

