Chemistry: bicarbonate, bilirubin (total and direct), blood urea nitrogen, calcium, chloride, cholesterol (total, high-density lipoprotein, and calculated low-density lipoprotein), creatine phosphokinase, creatinine, gamma-glutamyltransferase, globulin, glucose, lactate dehydrogenase, magnesium, phosphorus, potassium, sodium, total protein, triglycerides, troponin I, uric acid, and C-reactive protein

Urinalysis: Appearance, bilirubin, color, glucose, ketones, leukocyte esterase, microscopy (performed if dipstick is positive; includes bacteria, casts, crystals, epithelial cells, red blood cells, and white blood cells), nitrites, occult blood (for urine microscopy), pH, protein, specific gravity, and urobilinogen

Pregnancy: Urine dipstick pregnancy test except at screening

In cases of abnormal urinalysis results, urine microscopy will be performed.

Abnormal clinical laboratory values will be flagged as either high or low (or normal or abnormal) based on the reference ranges for each laboratory parameter. The Investigator will determine whether any abnormally high or low results are clinically significant or not clinically significant. Clinical significance is defined as any variation in results that has medical relevance and may result in an alteration in medical care (eg, active observation, diagnostic measures, or therapeutic measures).

If a clinically significant change from the screening value is noted, the clinically significant value and the reason for clinical significance will be documented on the AE page of the subject's eCRF, even if asymptomatic. The Investigator will continue to monitor the subject with additional assessments until the values have reached either the reference range or the values at screening or until the Investigator determines that follow-up is no longer medically necessary.

The US Food and Drug Administration (FDA) guidance for industry on Drug-Induced Liver Injury: Premarketing Clinical Evaluation (July 2009) will be used as a guideline for the assessment of liver enzymes/liver function tests (DHHS 2009).

Clinically significant laboratory values for individual subjects will be listed. A summary for the numbers and percentages of subjects with clinically significant laboratory values at any time point will be presented.

All laboratory specimen (clinical and bioanalysis) analysis, details in storage and shipment will be followed according to the laboratory manual.

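### Protocol 6.9 exempts some RA-attributed safety findings from AE and SAE reporting, while 6.4.2–6.4.4, 6.4.5.3 and 6.4.5.4 require the same findings to be recorded

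*Protocol*

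**What the plan says.** Protocol 6.9 opens with a general rule. Abnormal laboratory results and other safety assessments (ECGs, radiology and vital signs are its examples) "felt to be clinically significant in the medical and scientific judgment of the Investigator are to be recorded as AEs or SAEs". Its second paragraph takes part of this back. It excludes from reporting, as AEs or as SAEs, "any clinically significant safety assessments that are associated with the underlying disease, unless judged by the Investigator to be more severe than expected".

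Other current sections give the instruction without that exemption:

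- **6.4.4 (laboratory).** After a clinically significant change from screening, "the clinically significant value and the reason for clinical significance will be documented on the AE page of the subject's eCRF, even if asymptomatic". Sections 6.4.2 (vital signs) and 6.4.3 (ECGs) also send such changes to the AE page.
- **6.4.5.1.** The AE definition includes abnormal laboratory findings and has no exclusion for the disease under study.
- **6.4.5.3.** All SAEs after signature of the consent form must be reported. AEs identified from any study data are documented on the AE page.
- **6.4.5.4.** AEs resulting from "reactions to concurrent medications, or progression of disease states must also be reported". A condition present at screening becomes an AE if it deteriorates at any time.

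None of these refers to 6.9, and 6.9 does not refer to them. SAP 9.1 tabulates TEAEs and SAEs and has no rule for disease-related findings.

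**The concern.** Incidence of AEs, withdrawals due to AEs and SAEs are part of a secondary endpoint (Protocol 7.2). The potential risks named in Protocol 1.5 include immune, liver-enzyme and cardiovascular effects, which laboratory tests, ECGs and vital signs help to detect. If one site follows 6.4.4 and another follows 6.9, the same result becomes an AE at the first and not at the second. The two judgements that decide it, association with RA and severity beyond expectation, are not defined.

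Reporting is affected as well as tabulation. Under 6.4.5.5 an SAE reaches pharmacovigilance through the AE page, and under 6.4.5.6 the sponsor can upgrade an assessment of seriousness or causality. Neither can act on a finding that was never entered. The study has no safety monitoring committee (6.7) and no external data monitoring committee (11.1.1).

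**Working it through.** The plan gives no figure to reproduce, so the check is a comparison of texts. Each kind of finding is put to both sets of rules.

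| Finding | 6.4.2–6.4.4, 6.4.5.3, 6.4.5.4 | 6.9 | Conflict? |
|---|---|---|---|
| A. Attributed to RA, present at screening, not deteriorated | Not an AE (6.4.5.4) | Not reported, unless worse than expected | None in the ordinary case |
| B. Clinically significant change from screening, not attributed to RA | Record | Record | None |
| C. Clinically significant change attributed to background RA medication | Record (6.4.5.4, concurrent medications) | Record; the exemption names the disease, not its treatment | None |
| D. Clinically significant change attributed to RA, judged worse than expected | Record | Record | None |
| E. Clinically significant change attributed to RA, judged no worse than expected | Record | Do not report | Direct |
| F. As E, and meeting a seriousness criterion | Report as SAE (6.4.5.3) | Do not report as SAE | Direct |

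1. Rows A to D give one answer. The conflict is confined to rows E and F.
2. In row E a site cannot comply with both texts. Section 6.4.4 does not ask why the value changed, and 6.4.5.4 applies no severity threshold to deterioration.
3. Row F is narrower, but 6.9 names SAEs expressly while 6.4.5.3 says all.
4. For imaging there is no counterpart in 6.4.2–6.4.4, so the conflict there is with 6.4.5.3 and 6.4.5.4 only.
5. Scale: in an arm of 37, one subject with no other AE who moves in or out of the AE table changes incidence by 1/37 = 2.7 percentage points. The number of subjects in rows E and F cannot be derived. The documents give neither a rate of clinically significant changes nor the share that would be attributed to RA.
6. Outputs that do not depend on an AE record are untouched. These are the summary of subjects with clinically significant laboratory values (Protocol 6.4.4), the laboratory summaries and shift tables (SAP 9.3), the vital-sign summaries and shifts (SAP 9.4), and the ECG summaries, interpretation shifts and QTcF threshold counts (SAP 9.6).

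**The case against.** The strongest defence is that 6.9 is a specific qualification of general rules and has a sensible purpose. CRP and ESR are in the routine laboratory panel (6.4.4), and entry requires hsCRP of at least 6.0 mg/L. Without some exemption, a clinically significant rise in an inflammatory marker becomes an AE, possibly more often on placebo, and efficacy leaks into the safety tables. This purpose is reasonable and any fix should respect it. It does not settle the conflict. The text reaches every laboratory, ECG, imaging and vital-sign result, and no cross-reference tells a site that 6.9 overrides the other sections.

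It is also fair to say that a result meeting a seriousness criterion would seldom be judged no worse than expected, so row F should be uncommon. AE tables are descriptive, and blinding limits systematic differences between arms. It does not exclude them, since attribution to RA could follow disease activity.

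Several stronger readings are tempting but not supported:

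- A reader might infer a direct conflict with 6.4.5.8, where of the causality assessment it is said that "it is not a factor in determining what is or is not reported in the study". That concerns relationship to study drug, whereas 6.9 turns on association with RA, a different judgement. Its instruction to report in cases of doubt leans the same way but does not make a contradiction.
- A reader might infer a blanket bar on RA-attributed findings. Row D remains reportable.
- A reader might infer that laboratory abnormalities can be left out by blaming background csDMARDs. Row C shows otherwise.
- A reader might infer that safety signals disappear. Measured values are still summarised, and 6.4.5.6 defines hepatotoxicity and febrile neutropenia numerically as events of special interest, with hepatotoxicity also going on a dedicated eCRF.

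**Conclusion.** The contradiction stands in the current protocol text for one class of finding: a clinically significant change attributed to RA and judged no worse than expected. AE and SAE counts that arise from safety assessments can therefore depend on which section a site follows. Counts from other clinical events, and summaries of measured values, are not affected. No size can be put on the effect from the documents; the 2.7 points per subject is a unit of scale, not an estimate. The conclusion rests on the wording alone, and on the absence of any cross-reference or SAP rule that ranks one section above another. It is a modest but real defect in a secondary safety endpoint.

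**What to change.** Reconcile 6.9 with 6.4.2–6.4.4, 6.4.5.3 and 6.4.5.4 into one reporting rule, and place SAEs outside any disease-related exemption.

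The preferred form replaces the second paragraph of 6.9. All clinically significant findings are recorded, with an eCRF flag for those the investigator considers consistent with underlying RA. SAP 9.1 then tabulates TEAEs with and without flagged events, so that disease-activity markers such as CRP and ESR do not blur the safety comparison.

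If the sponsor prefers to keep an exemption for non-serious findings, 6.9 should name the exempt findings, and the other sections should cross-refer to it. This also removes the contradiction, but the exempted findings then cannot be recovered for the AE tables.

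The preferred form costs protocol and SAP wording, one eCRF field and a few more AE records.
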